### 13.3 Disease Parameters

**Measurable disease:** Bi-dimensionally measurable lesions with clearly defined margins by MRI scan. All tumor measurements must be recorded in millimeters (or decimal fractions of centimeters).

**Non-measurable or evaluable disease:** Uni-dimensionally measurable lesions or lesions with margins not clearly defined such as areas of T2/FLAIR signal abnormality or poorly defined enhancing abnormality.

Note: For cystic lesions, the only measurable part is any enhancement area around the

cyst that is clearly defined and bi-dimensionally measurable. The cyst itself should not be considered measurable or non-measurable disease.

**Target lesions:** All measurable lesions that are residual of the lesion treated with MLA should be identified as target lesions and recorded and measured. Target lesions should be selected on the basis of their size (lesions with the longest diameter), but in addition should be those that lend themselves to reproducible repeated measurements. It may be the case that, on occasion, the largest lesion does not lend itself to reproducible measurement in which circumstance the next largest lesion, which can be measured reproducibly should be selected. When there are too many measurable lesions, choose the largest 3 lesions as target lesions to follow. The other measurable lesions should be considered evaluable for the purpose of objective status determination.

**Non-target lesions:** All non-measurable lesions should be identified as non-target lesions and should also be recorded at baseline. Measurements of these lesions are not required, but the presence, absence, or in rare cases unequivocal progression of each should be noted throughout follow-up.

### 13.4 Methods for Evaluation of Measurable Disease

All measurements should be taken and recorded in metric notation using a ruler.

**Clinical lesions:** Clinical lesions will only be considered measurable on brain MRI when they are  $\geq 5$  mm diameter as assessed using a ruler.

**Histology:** This technique can be used to differentiate between partial responses (PR) and complete responses (CR) in rare cases when biopsy or surgical resection of a measurable lesion is clinically indicated.

**Perfusion/CBV:** This advanced brain MRI technique can be used as an adjunct test to determine treatment response or disease status. However, it should not be used as the primary or sole method to determine response or disease status.

#### 13.4.1 Evaluation of Target Lesions

**Complete Response (CR):** Disappearance of all target lesions.

**Partial Response (PR):**  $\geq 50\%$  decrease compared with baseline in the sum of products of perpendicular diameters of all target lesions sustained for at least 4 weeks.

**Progressive Disease (PD):** At least a 25% increase in the sum of products of perpendicular diameters of at least 1 target lesion, taking as reference the smallest sum of products of perpendicular diameters on study (this includes the baseline sum if that is the smallest on study). The absolute increase in any dimension must be at least 5mm when calculating the products of perpendicular diameters.

**Stable Disease (SD):** Neither sufficient shrinkage to qualify for PR nor sufficient increase to qualify for PD, taking as reference the smallest sum of products of perpendicular diameters while on study.

### 13.4.2 Evaluation of Non-Target Lesions

**Complete Response (CR):** Disappearance of all non-target lesions.

**Non-CR/Non-PD:** Persistence of one or more non-target lesion(s).

**Progressive Disease (PD):** Appearance of one or more new lesions and/or unequivocal progression of existing non-target lesions on stable or increasing doses of corticosteroids compared with baseline scan or best response after initiation of therapy not caused by comorbid events (e.g. radiation therapy, demyelination, ischemic injury, infection, seizures, postoperative changes, or other treatment effects). Unequivocal progression should not normally trump target lesion status. It must be representative of overall disease status change, not a single lesion increase.

Although a clear progression of “non-target” lesions only is exceptional, the opinion of the treating physician should prevail in such circumstances, and the progression status should be confirmed at a later time by the review panel (or Principal Investigator).

### 13.4.3 Evaluation of Best Overall Response

The best overall response is the best response recorded from the start of the treatment until disease progression/recurrence (taking as reference for progressive disease the smallest measurements recorded since the treatment started). The patient's best response assignment will depend on the achievement of both measurement and confirmation criteria.

Summary of the RANO Response Criteria (Adapted from [47])

Criterion	CR	PR	SD	PD
T1 gadolinium enhancing disease	None	$\geq 50\% \downarrow$	$< 50\% \downarrow$ but $< 25\% \uparrow$	$\geq 25\% \uparrow^*$
T2/FLAIR	Stable or $\downarrow$	Stable or $\downarrow$	Stable or $\downarrow$	$\uparrow^*$
New lesion	None	None	None	Present*
Corticosteroids	None	Stable or $\downarrow$	Stable or $\downarrow$	NA†
Clinical status	Stable or $\uparrow$	Stable or $\uparrow$	Stable or $\uparrow$	$\downarrow^*$
Requirement for response	All	All	All	Any*

Abbreviations: RANO, Response Assessment in Neuro-Oncology; CR, complete response; PR, partial response; SD, stable disease; PD, progressive disease; FLAIR, fluid-attenuated inversion recovery; NA, not applicable.

\* Progression occurs when this criterion is present.

† Increase in corticosteroids alone will not be taken into account in determining progression in the absence of persistent clinical deterioration.

### 13.4.4 Duration of Response

**Duration of overall response:** The duration of overall response is measured from the time measurement criteria are met for CR or PR (whichever is first recorded) until the first date that recurrent or progressive disease is objectively documented

(taking as reference for progressive disease the smallest measurements recorded since the treatment started).

The duration of overall CR is measured from the time measurement criteria are first met for CR until the first date that progressive disease is objectively documented.

**Duration of stable disease:** Stable disease is measured from the start of the treatment until the criteria for progression are met, taking as reference the smallest measurements recorded since the treatment started, including the baseline measurements.

#### **13.4.5 Neurological Exam and Performance Status**

Patients will be graded using the Karnofsky Performance Status scale and their neurological function evaluated as improved, stable or deteriorated in addition to objective measurement of tumor size. These parameters will be used to determine the overall response assessment.

#### **13.4.6 Progression-Free Survival**

PFS is defined as the duration of time from start of treatment to time of progression or death, whichever occurs first.

### **14 AUDITING**

As coordinating center of this trial, Washington University (via the Quality Assurance and Safety Monitoring Committee (QASMC) will monitor each participating site to ensure that all protocol requirements are being met; that applicable federal regulations are being followed; and that best practices for patient safety and data collection are being followed per protocol. Participating sites will be asked to send copies of all audit materials, including source documentation. The audit notification will be sent to the Washington University Research Patient Coordinator, who will obtain the audit materials from the participating institution.

Notification of an upcoming audit will be sent to the research team one month ahead of the audit. Once accrual numbers are confirmed, and approximately 30 days prior to the audit, a list of the cases selected for review (up to 10 for each site) will be sent to the research team. However, if during the audit the need arises to review cases not initially selected, the research team will be asked to provide the additional charts within two working days.

Items to be evaluated include:

- Subject screening and enrollment
- Reporting of adverse events
- Maintenance of HIPAA compliance
- Completeness of regulatory documentation
- Completeness of participant documentation
- Acquisition of informed consent
- IRB documentation
- Issues of protocol adherence

Additional details regarding the auditing policies and procedures can be found at <https://siteman.wustl.edu/research/clinical-research-resources/protocol-office-prmcqasmc/>.

## 15 STATISTICAL CONSIDERATIONS

### 15.1 Study Design

This is a single-center study consisting of a phase I study to identify MTD (/RP2D and a phase II placebo-controlled randomized study on target patients. In the phase I study, MTD will be determined and a recommended phase 2 dose (RP2D) will be decided. The maximum tolerated dose (MTD) is defined as the dose level immediately below the non-tolerated dose. A total of at least 6 patients must be treated at a dose level for it to be considered the MTD. RP2D is the dose recommended for phase 2 study based on the MTD from dose escalation and ALC data which can never exceed MTD.

During the randomized phase II portion of the study, eligible patients will be enrolled and randomized at a 1:1 ratio to either rhIL-7-hyFc at the RP2D dose level or placebo arm (see study Schema).

Phase I enrollment was completed with N=19 patients. The MTD was identified as 720 mcg/kg. Current collected data suggest an improvement in progression-free survival in patients with IDH1 wildtype as defined by immunohistochemistry negative staining using an IDH mutant-specific antibody and MGMT promoter unmethylated GBM; therefore, we have added an expansion cohort to the rhIL-7-hyFc arm with N=31 as justified in Section 14.4.

### 15.2 The phase I study

#### 15.2.1 Study design

The phase I dose finding study will begin with an Accelerated Phase with 1 patient per cohort at the first 2 doses (60 mcg/kg, 120 mcg/kg) followed by a conventional 3+3 dose escalation phase on the remaining 4 doses (240 mcg/kg~960mcg/kg). A cohort of six patients need to be tested at the MTD/RP2D level.

#### The Accelerated Phase

The Safety data from current phase I studies on rhIL-7-hyFc in solid tumors and GBM show that patients tolerate either or both of the first 2 doses (60 mcg/kg, 120 mcg/kg) well with no DLTs observed at the 2 doses, see rationale section on ABTC-1403 (IND 137067) on healthy volunteers, GX-I7-CA-003 in solid tumors, GX-I7-CA-004 in GBM. The Accelerated Phase will be conducted for dose levels 1 to 2, i.e., dosage 60 mcg/kg and 120 mcg/kg, with 1 patient per dose level and DLT and adverse events will be monitored during the 1st cycle of the treatment. If no DLT is observed at dosage 60 mcg/kg, a new patient will be enrolled to dose level 2 (120 mcg/kg). If any DLTs are observed in the 1 patient at either of the two dose levels, the Accelerated Phase will convert to a conventional 3+3 design at the dose level where DLTs are observed and remain so for all the dose levels above. If excess DLTs (>=2 out of a total of 6 patients experiencing DLTs) are observed at dose level 1 (60 mcg/kg), the study will halt. If no DLTs, the phase I

study will proceed to the next conventional 3+3 phase for dose levels 3 to 6 (see dosage Table in Section 5.2).

### **The conventional 3+3 Phase**

Assuming no conversion at the first 2 doses, the conventional 3+3 design with 3 independent patients per cohort will start at dose level 3 (240 mcg/kg) and will follow the dose escalation decision rule of 3+3 design to escalate along the dosages from dose level 3 (240 mcg/kg) to 6 (960 mcg/kg) sequentially from the lowest to the highest dose level, see dosage Table in Section 5.2. The dose escalation rules are summarized in the dose escalation criteria in Section 5.3.3. If excess DLT ( $\geq 2$  out of a cohort of 3 patients or  $\geq 2$  out of a total of 6 patients from 2 cohorts) is observed at starting dose level 240 mcg/kg, a cohort of 5 patients (six, plus the one patient tested previously) will be tested at dose level 2 (120 mcg/kg) and if  $\leq 1$  DLTs in 6 are observed, dose level 2 will be the recommended dose for the Phase II. If  $\geq 2$  out of 6 patients are observed with DLTs at dose level 2, the trial will similarly test dose level 1 to have dose level 1 either as the MTD or the study halt in presence of excess toxicities. If no excess dose (0 DLT out of a cohort of 3 patients or 1 DLT out of a total of 6 patients) is observed at dose level 3, the Phase I study will follow the dose escalation decision rule to escalate along the dosages thereafter to dose level 6 until the MTD if no DLT at highest dose level) is identified at which no more than one in six patients experiences DLT. A total of 6 patients will need to be treated at the MTD level. Integrating the MTD data and ALC data, a RP2D (which can be the MTD or not but will not exceed the MTD), will be determined.

If we do not find MTD at the proposed dose levels, we plan to amend the protocol to test new or higher dose levels per the recommendations from NIT. In addition, another Phase I trial is on-going. Dose escalation can be stopped if a MTD is determined through the on-going Phase I trial announced by the sponsor.

#### **15.2.2 Endpoint**

The primary endpoint of the phase I is adverse events (AEs), especially dose limiting toxicity (DLT). DLT will be defined as  $\geq$  grade 3 AEs that occur within 30 days from the date when patients receive the 1st dose of rhIL-7-hyFc administration and are concluded to be possibly, likely or definitely related to the drug regimen that occurs during cycle 1, with severity graded according to the Common Terminology Criteria for Adverse Events (CTCAE) 5.0. Grade 3 dermatologic AEs, including injection site reaction, that resolves to Grade  $\leq 2$  in  $\leq 3$  days with supportive care; transient Grade 3 influenza-like symptoms or pyrexia controlled with medical management; Grade 3 fatigue that resolves to Grade  $\leq 2$  in  $\leq 3$  days; Grade 3 neurologic toxicity responding within  $\leq 7$  days to steroids, anticonvulsants, or electrolyte correction; or Grade 3 laboratory abnormalities that are asymptomatic and considered by the investigator not to be clinically significant will be excluded from the DLT definition.

The secondary endpoint is absolute lymphocyte count (ALC).

### **15.2.3 Sample size calculation**

During the Phase I, total number of patients enrolled will depend on the number of dose levels and observed DLTs, ranging from a minimal of 6 patients to a maximum of 26 patients.

### **15.2.4 Statistical Analysis**

Data from the Phase I study will be presented in a descriptive manner AEs and SAEs will be summarized by counts and percentages by patient, dose type and grade.

## **15.3 The randomized phase II study**

### **15.3.1 Study design**

For the phase II trial, eligible patients, stratified by concomitant use of steroids (Yes/No), will be randomized at a 1:1 ratio to receive either placebo or the study drug rhIL-7-hyFc. Patients on the study drug arm will receive multiple doses of the study drug rhIL-7-hyFc (see study schema). Lymphocyte count will be measured before and after rhIL-7-hyFc administration (details see treatment schema and study calendar).

### **15.3.2 Endpoint**

The primary endpoint of Phase II is the % increase of ALC in evaluable patients prior to adjuvant TMZ (at ~ Week 4) that measures the “pure” drug effect before influences from TMZ in reference to the baseline prior to rhIL-7-hyFc injection. A patient is considered evaluable for the primary endpoint if (s)he completes CBC at baseline and at ~4 weeks after the first dose of NT-17 or placebo and has valid ALC measurements prior to and at ~week 4 before adjuvant TMZ of treatment with NT-17 or placebo. Enrolled patients who are not evaluable for the primary endpoint will be replaced so as to meet the study power requirements (see 15.3.3).

The secondary endpoints include lymphocyte counts over time in the setting of steroid use and chemotherapy, progression free survival (PFS) and overall survival (OS).

### **15.3.3 Sample size calculation**

We summarized the ALC of all comers seen in our center at 1 month after completion of RT + TMZ and estimated a mean of ALC at 850 and a standard deviation (SD) of 480. This also agrees with data in published literatures (Mendez 2016). We assume that patients on the placebo arm (who usually have received radiation and TMZ post-operative) have the same mean of 850 and SD of 480. Based on 1-sided two sample t-test with equal variance at a 5% level, 8 patients per arm provides 80% power to test a mean ALC of 1486 in the treated patients in comparison to a mean of 850 in the placebo arm. Assuming ~10% dropout rate, we will enroll a total of 20 patients, 10 per arm.

For the whole study spanning through the Phase I and the Phase II study, approximately a minimum of 26 to a maximum of 46 evaluable patients will be enrolled.

#### **15.3.4 Accrual**

We see approximately 150 new patients with HGG (with ~70% are GBM) each year at Washington University with ~30% participating in clinical trials. We expect to be able to enroll approximately 1-2 patient per month on average, and thus it will take approximately 18 months to enroll ~29 patients and 30 months to enroll the expected maximum total of 46 evaluable patients.

#### **15.3.5 Statistical Analysis**

All data will be analyzed as observed and no imputation for missing values will be used. Patient characteristics will be summarized by descriptive statistics. Descriptive statistics will be used to summarize the trial results, i.e., statistics for continuous variables such as lymphocyte counts may include means, medians, ranges and appropriate measures of variability. Qualitative variables will be summarized by counts and percentages. The uncertainty of estimates will be assessed by confidence intervals (CIs). Markers for lymphocyte recovery in each group will be summarized as means and standard deviations (SD) at each time point. The primary endpoint, ALC at ~ week 4 and the change from the time point of radiation will be compared between the two arms by two sample t-test or Wilcoxon rank sum test as appropriate and by a linear model where other important factors such as concomitant use of steroid besides the treatment arm will be modeled. Within each arm, the primary endpoint will be compared to the ALC at the completion of radiation by paired sample t-test or Wilcoxon signed rank test as proper. Total lymphocyte counts at later cycles will be similarly analyzed but may be compared to a different reference time point. We will analyze ALC over time using linear models for repeated measurement data, followed by post-hoc multiple comparisons for between-group differences at other time points of interest. PFS and overall survival will be analyzed using the Kaplan–Meier method and survival difference will be compared between arms by log rank test. The univariate Cox proportional hazard model will be applied to evaluate ALC at each time point, in continuous scale and dichotomized scale by the cutoff of 1 (determined based on literature), for their prognostic effect on PFS and OS while multivariate Cox model will be applied to account for other covariates. The time varying Cox proportional hazard model will be applied to model the prognostic effect of the longitudinal ALC as a whole, without and with additional covariates.

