#### **4.4 Randomization**

A total of 20 patients during phase II will be randomized 1:1 to receive either placebo or rhIL-7hyFc at the dose determined during phase I. Patients will be stratified by concomitant use of steroids (Yes/No). This study is double-blinded (participant, and physician/study coordinator are all blinded; pharmacist and study statistician are not blinded). Approximately equal number of patients will be assigned to each treatment group. The randomization will be performed in OnCore. Randomization will occur on eligible patients only and is auto generated after the eligibility is confirmed, the patient has an on-study date, and the strata steroid use (Yes/No) is confirmed; which will return either an 'A' or 'B' assignment. Only the pharmacist and statistician will know the treatment corresponding to each assignment.

Patients enrolled to the phase II expansion cohort will not be randomized.

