### **Discontinuation Rules and Procedures for rhIL-7-hyFc-Related Adverse Events**

Toxicity	Hold Treatment for Grade	Guidance for Restarting	Guidance for Permanent Discontinuation	Supportive Care Guidelines
Immune mediated Myocarditis	2 - 4	NA	
 
• Permanently discontinue
 
	
 
• Initiate treatment as per institutional guidelines and consider
 

Toxicity	Hold Treatment for Grade	Guidance for Restarting	Guidance for Permanent Discontinuation	Supportive Care Guidelines
				antiarrhythmic drugs, temporary pacemaker, ECMO, or VAD as appropriate.
AST/ALT or bilirubin increase/ immune-related hepatitis	2	Monitor frequently Related: reduce by 1 dose level Unrelated: same dose level	
 
AST or ALT <math>> 5 \times</math> ULN or total bilirubin <math>> 3 \times</math> ULN
 
Toxicity fails to resolve within 12 weeks of last dose of rhIL-7-hyFc
 
Permanently discontinue for liver enzyme elevations meeting criteria for Hy's Law
 
	
 
Monitor LFT results frequently (consider weekly)
 
Treat with IV or oral corticosteroids
 

	3/4	N/A	
 
Permanently discontinue
 
	
 
Treat with IV corticosteroids for 24 to 48 hours. When symptoms resolve to <math>\leq</math> Grade 1, taper steroids over no less than 4 weeks
 

Rash/dermatitis	2	Consider interrupting for Grade 2 for $> 1$ week		
 
Start topical emollients, mild-strength corticosteroid cream
 

	3	Toxicity resolves to Grade 0-1 Related: reduce by 1 dose level Unrelated: same dose level	
 
Toxicity fails to resolve within 12 weeks of last dose or inability to reduce corticosteroids to <math>\leq 10</math> mg of prednisone or equivalent per day within 12 weeks
 
	
 
Start topical emollients, antihistamines, and high-strength corticosteroid cream
 
Consider to administer oral corticosteroids
 

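### Section 15.3.5 names no primary test for the randomized ALC comparison and no model that adjusts for baseline ALC; a prespecified log ANCOVA would be more efficient, by roughly 0 to 10 power points

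*Combined protocol and SAP*

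**What the plan says.** Section 15.3.2 makes the primary endpoint the percentage increase in ALC at about week 4, before adjuvant TMZ, relative to the pre-injection value. A patient is evaluable if he or she "completes CBC at baseline and at ~4 weeks after the first dose" of study drug or placebo and both ALC values are valid.

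Section 15.3.5 gives the comparison. Week-4 ALC and a change, here referenced to the time point of radiation, "will be compared between the two arms by two sample t-test or Wilcoxon rank sum test as appropriate". The same sentence adds a linear model containing arm and other important factors, with concomitant steroid use as the only example. No analysis is labelled primary, the rule for choosing between t-test and Wilcoxon is not given, and baseline ALC is not listed as a covariate.

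Section 4.4 states "Patients will be stratified by concomitant use of steroids (Yes/No"), confirmed before the assignment is generated. It also says that the study statistician is not blinded.

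The sample size in 15.3.3 rests on raw ALC: "Based on 1-sided two sample t-test with equal variance at a 5% level, 8 patients per arm provides 80% power" for "a mean ALC of 1486 in the treated patients in comparison to a mean of 850 in the placebo arm".

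**The concern.** Every evaluable patient has a baseline count, and in a 20-patient trial that count is likely to be one of the strongest predictors of the week-4 count. Percentage change divides the outcome by a single noisy baseline measurement. This skews the outcome and carries the baseline's error into it. When the two counts are only weakly correlated, the division can cost more precision than it recovers. Covariate adjustment instead estimates how much weight baseline deserves, and it removes the part of any chance baseline imbalance that predicts outcome.

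The second issue is choice. With three candidate analyses, none named as primary, and an unblinded statistician, the result to be reported as the trial's answer is not fixed in advance.

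**Working it through.** **1. The plan's own figure.** Inputs from 15.3.3: means 1486 and 850, so the difference is 636; the placebo arm is assumed to "have the same mean of 850 and SD of 480"; 8 per arm; one-sided 5%; equal variance. Noncentrality = 636/(480 × √(2/8)) = 636/240 = 2.65 on 14 df. Exact power is 80.9%, which reproduces the stated 80%. At 10 per arm, noncentrality = 636/(480 × √(2/10)) = 2.96 on 18 df, and power is 88.6%. These figures are for raw week-4 ALC, not for % increase.

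**2. Model for the % change scale.** The plan gives no SD for % change and no baseline/week-4 correlation, so a model must be assumed. ALC is taken as lognormal with mean 850 and SD 480 at both times:
- log SD = √ln(1 + (480/850)²) = √ln(1.319) = 0.526;
- log mean = ln 850 − 0.526²/2 = 6.607;
- treatment multiplies week-4 ALC by 1486/850 = 1.748;
- baseline and week-4 log counts have correlation r, taken as 0.3, 0.5, 0.7 or 0.8;
- test at one-sided 5%, as in 15.3.3, with 10 per arm.

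The two tests are a t-test on (week 4 − baseline)/baseline, and the arm coefficient in a linear model of log week-4 ALC on arm and log baseline ALC.

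**3. Simulated power, no entry limit, 10 per arm.**

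| r (assumed) | % change t-test | log ANCOVA | gain |
|---|---|---|---|
| 0.3 | 56% | 75% | 19 |
| 0.5 | 70% | 82% | 12 |
| 0.7 | 89% | 93% | 4 |
| 0.8 | 97% | 98% | 1 |

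At r = 0.3 a t-test on raw week-4 ALC has 70% power in this model, so % change does worse there than ignoring baseline. The Wilcoxon test on % change stays within about 3 points of the t-test. Type I error is about 5% for all methods.

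**4. Entry limit.** Section 3.1 requires ALC ≥ 600/mcL for the randomized part. In the assumed distribution, (ln 600 − 6.607)/0.526 = −0.40, so about 34% of baselines would fall below the limit. These are the low denominators that make % change unstable. With baseline truncated at 600 (r being the correlation before truncation), the gain is about **10/6/1/0 points** for r = 0.3/0.5/0.7/0.8. Repeat runs differ by about a point at 0.5 and 0.7. Truncation is an approximation, because eligibility uses the screening value and baseline is the Week 1 Day 1 value (10.1).

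**5. Steroid term.** Adding a steroid indicator unrelated to ALC reduces the truncated gain to about 7/3/0/0. The cost is smaller when strata are evenly split between arms, which stratified randomization aims for. If steroid use does predict ALC, the term can recover its cost.

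**6. If raw week-4 ALC were the primary comparison.** On the plan's equal-variance normal model, ANCOVA has residual SD 480 × √(1 − r²) and loses 1 df. At r = 0.5 this is 480 × 0.866 = 416; noncentrality = 636/(416 × 0.447) = 3.42 on 17 df; power is 94.9% against 88.6%. The gain is about 2/6/10/11 points for r = 0.3/0.5/0.7/0.8. Simulation, which allows for chance baseline imbalance, gives about 5 points at r = 0.5 (93.9% against 88.7%).

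**The case against.** The plan is not as bare as the t-test wording suggests, and several stronger readings fail.

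- **That the steroid stratum is ignored.** A reader who stops at the t-test might infer this. The sentence goes on to a linear model with steroid use, so an adjusted between-arm analysis is planned.
- **That baseline ALC is ignored.** The % increase endpoint uses each patient's baseline, and the linear model's covariate list is open-ended. What is missing is baseline as a named covariate.
- **That the trial loses 19 points of power.** That gap appears only at an assumed r = 0.3 with no entry limit. It roughly halves with the limit and nearly vanishes at r = 0.8 either way. The lognormal model also lets the treated SD rise to 480 × 1.748 = 839, whereas 15.3.3 assumes equal variance.
- **That the model adjusts for post-dose steroids.** The toxicity table in 6.2 does include "Treat with IV or oral corticosteroids", so coding steroid use after dosing would adjust for something treatment can affect. But 4.4 and 15.3.1 use essentially the same phrase for the pre-randomization stratum, which is the natural reading of 15.3.5. This is a wording risk, not a shown error.

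It is also fair to say that the planned tests are valid and that the stated power reproduces on the plan's assumptions. None of this identifies the primary analysis or adds baseline as a covariate.

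**Conclusion.** The point holds as one of efficiency and prespecification. Section 15.3.5 offers a t-test, a Wilcoxon test and a linear model without ranking them, and does not name baseline ALC as a covariate. With the entry limit respected, log ANCOVA gains about 10 points over the % change t-test at r = 0.3, about 6 at 0.5, and next to nothing at 0.7 or above, less up to about 3 points for an uninformative steroid term. The size rests on the lognormal form, on applying the plan's 850 and 480 to both time points, and on a correlation that the documents do not give. The documents do not support a claim of inflated type I error or of a fixed 19-point loss. The change is worth making because it costs almost nothing and also settles which result counts.

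**What to change.** In 15.3.5, name one primary analysis: a linear model of log week-4 ALC on arm, log Week 1 Day 1 ALC, and the steroid stratum as recorded at randomization, with post-dose steroid use excluded. Report the arm effect as a ratio of geometric means, expressed as an adjusted percentage difference, with its confidence interval. Keep the t-test and Wilcoxon test as supportive, and bring the endpoint wording in 15.3.2 and 15.3.5 into line with the model.

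Cost: one paragraph of text and two degrees of freedom (18 to 16 with 10 per arm). All the data are already collected. The summary also changes, from a difference in mean percentage increase to a ratio of geometric means, so the text should say so; mean % increase can still be shown descriptively.
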